### 5.2.1 Phase 3 Testing Strategy

The overall alpha for the Phase 3 study is 0.05 (two-sided).

For the Phase 3 study, type I error control across endpoints will be performed hierarchically (see [Figure 5.2.1-1](#)). The primary analysis is for PFS. If that analysis is significantly superior, then the secondary endpoints may be tested in the order of OS followed by ORR. That is, if the results comparing PFS between treatment groups are significant at the applicable alpha level, then results comparing OS between treatment groups will be interpreted. If the results comparing OS between treatment groups are significant, then results comparing ORR between treatment groups will be interpreted. Other endpoints will not be tested formally.

**Figure 5.2.1-1: Phase 3 Hierarchical Procedure with Group Sequential Testing in All Randomized Subjects**

Approximately 700 subjects will be randomized in 1:1 ratio to BMS-986213 or nivolumab monotherapy arm respectively.

- Approximately 365 PFS events in all randomized subjects will provide around 85% power to detect an average HR of 0.73 with an overall type I error of 5.0% (two-sided). The target hazard ratio was obtained via simulation using above modeling.

Table 5.2.1-1 summarizes the analysis of PFS in Phase 3. The interim PFS analysis (PFS IA) will be performed when a minimum follow-up of 12 weeks is achieved for approximately 400 randomized subjects or at least 150 PFS events have been observed per BICR. PFS IA will determine whether the study stops at Phase 2 (PFS HR > 0.8) or continues as Phase 3 (PFS HR ≤ 0.8). An administrative alpha penalty of 0.001 will be used for the PFS IA, although there is no plan to stop for efficacy at that analysis.

If PFS IA meets the pre-specified threshold and the study proceeds to Phase 3, the final PFS analysis will be performed when at least 365 PFS events have occurred per BICR and will use all remaining unspent alpha.

**Table 5.2.1-1: Schedule of Analyses of Primary Endpoint**

	Interim PFS Analysis (PFS IA)	Final PFS Analysis (PFS FA)
Population	All randomized subjects	
Conditions	When 150 events of PFS are observed or all Phase 2 randomized subjects have been followed for at least 12 weeks (time of 1st scan)	When 365 events of PFS are observed
Expected timing	~15 months	~34 months
Nominal significance level	.001	0.049
Critical Hazard Ratio	HR ≤ 0.8*	HR ≤ 0.81

\*Not formally tested (administrative alpha); had to pass this boundary for the study to continue to Phase 3.

### Analysis of the Key Secondary Endpoint of OS

The first key secondary endpoint of OS will be formally compared using a hierarchical procedure using Lan-DeMets alpha spending function with the O’Brien-Fleming type of boundary in East v6 for each endpoint. This testing procedure is summarized in [Figure 5.2.1-1](#). OS will only be formally compared if the PFS FA analysis (primary endpoint) is statistically significant. This comparison could be either:

- a) at PFS FA (T2) that will occur when at least 365 (100%) PFS events are observed. We are estimating that approximately 210 (70%) of OS events will have occurred
- b) after 270 (90%) OS events have been observed (T3)
- c) after 300 (100%) OS events have been observed (T4).

The timing of OS IA2 is based on an estimate that it will be halfway between the first interim analysis of OS and the final OS analysis. The second key secondary endpoint of ORR will be formally compared using a hierarchical procedure. If the PFS (primary endpoint) and OS (first key secondary endpoint) analyses are statistically significant, ORR will be tested when it has matured. ORR will not be considered mature until all subjects have had the potential for 7 months of follow-up, which is the time of the third on-study scan.

**Table 5.2.1-2: Schedule of Analyses of OS, First Key Secondary Endpoint**

	Interim OS Analysis #1 (OS IA1)	Interim OS Analysis #2 (OS IA2)	Final OS Analysis OS FA
Population	All randomized subjects		
Assumed medians	Nivo mono arm: 36.9 months; BMS-986213 arm: 49.2 months		
Conditions*	At PFS FA (T 2 ) when ~ 210 (70%) OS events may be observed	After 270 (90%) OS events have been observed (T 3 )	After 300 (100%) OS events have been observed (T 4 )
Expected timing	~34 months (T 2 )	~42 months (T 3 )	~50 months (T 4 )
Nominal significance level (2-sided) - OS efficacy boundary	0.014	0.031	0.038
Cumulative alpha spent	0.014	0.036	0.049
Critical Hazard Ratio	HR ≤ 0. 713	HR ≤ 0. 0.769	HR ≤ 0.787
Cumulative Power	~36%	~60%	~69%

\* Primary condition for OS analysis is that the primary PFS endpoint analysis must be statistically significant before any formal comparison of OS.

Note: interim alpha spending and OS efficacy boundary will be determined based on the actual number of events/deaths at the time of database lock.

04AUG2021 Update to SAP: The primary endpoint analysis was tested on 09MAR2021 and it was statistically significant. The first interim analysis of OS (OS IA1) was performed at the same time by the DMC and it was not statistically significant. As pre-specified, the significant results for the primary endpoint led to unblinding at the subject level. OS and ORR, however, were not analyzed, nor summarized by treatment arm. The positive results of the PFS analysis led to submission of the data to health authorities. On 04AUG2021, the decision was made to unblind response data at the time of the second interim OS analysis (OS IA2), anticipated for OCT2021. ORR will be unblinded and reported descriptively until (and if) OS is statistically significant and then it will be tested according to the hierarchy.

25OCT2021 Update to SAP:

With a target of 270 deaths for the second interim analysis of OS (OS IA2), BMS observed 271 deaths in the blinded database on 30-AUG-2021. Consequently, BMS began preparing for a database lock planned to occur 19-OCT-2021, based on a standard 6-week timeline to allow time for final data cleaning, image reconciliation, and a survival sweep. During the course of that survival sweep, 20 additional deaths were entered into the database, resulting in 291 observed deaths as of 18-OCT-2021. Given that the target number of deaths for the final OS analysis (OS FA) is 300, BMS believes that it is impractical and unnecessary to perform an interim and final analysis so close together. The second interim analysis of OS will no longer be performed. We will proceed directly to the final OS analysis and all deaths in the database will be used in the analysis. As originally planned for the final OS analysis BMS, and not the DMC, will analyze the OS data and be unblinded to OS results.

Table 5.2.1-3 gives details on the alpha and critical hazard ratio if no second interim analysis is performed and there are 300 deaths at the time of lock. However, these will be calculated based on the actual data in the database at the time of lock.

**Table 5.2.1-3: Schedule of Analyses of OS in the Event that Second Interim Analysis Is Not Performed.**

	Interim OS Analysis #1 (OS IA1)	Final OS Analysis OS FA
Population	All randomized subjects	
Assumed medians	Nivo mono arm: 36.9 months; BMS-986213 arm: 49.2 months	
Conditions*	At PFS FA (T 2 ) 227 (75.7%) OS events were observed	Approximately 300 (100%) OS events have been observed
Nominal significance level (2-sided) OS efficacy boundary	0.019	0.043
Cumulative alpha spent	0.019	0.049
Critical Hazard Ratio	HR ≤ 0.733	HR ≤ 0.792
Cumulative Power	~43%	~69%

## 6 STUDY PERIODS, TREATMENT REGIMENS AND POPULATIONS FOR ANALYSES

### 6.1 Study Periods

Each treated subject will go through two study periods: baseline period and post baseline period.

- Baseline period:
    - Baseline evaluations or events will be defined as evaluations or events that occur before the date and time of the first dose of study treatment. Evaluations on the same date and time of the first dose of study treatment will be considered as baseline evaluations.
    - In cases where the time (onset time of event or evaluation time and dosing time) is missing or not collected, the following definitions will apply:
      - ◆ Pre-treatment AEs will be defined as AEs with an onset date prior to but not including the day of the first dose of study treatment
      - ◆ Baseline evaluations (laboratory tests, pulse oximetry and vital signs) will be defined as evaluations with a date on or prior to the day of first dose of study treatment
- If there are multiple valid assessments, the assessment that is closest to day (and time if collected) of the first dose of study treatment will be used as the baseline in the analyses. If multiple assessments are collected on the same date (and time, if collected), the last assessment will be considered as baseline.

- Post baseline period:
  - On-treatment AEs will be defined as AEs with an onset date and time on or after the date and time of the first dose of study treatment (or with an onset date on or after the day of first dose of study treatment if time is not collected or is missing). For subjects who are off study treatment, AEs will be included if event occurred within a safety window of 30 days (or 100 days depending on the analysis) after the last dose of study treatment. No “subtracting rule” will be applied when an AE occurs both pre-treatment and post-treatment with the same preferred term and grade.
  - On-treatment evaluations (laboratory tests, pulse oximetry and vital signs) will be defined as evaluations taken after the day (and time, if collected and not missing) of first dose of study treatment. For subjects who are off study treatment, evaluations should be within a safety window of 30 days (or 100 days depending on the analysis) after the last dose of study treatment.
  - If more than one tumor biopsy specimen is available, baseline PD-L1 and LAG-3 expression will be determined from the most recently collected specimen (prior to first dose of study treatment) with a measurable result

## 6.2 Treatment Regimens

The treatment group “as randomized” corresponds to the treatment group assigned by the IRT system.

- Arm A: Experimental arm: BMS-986213
- Arm B: Control arm: nivolumab

The treatment group “as treated” will be same as the treatment group “as randomized” by IRT unless a subject received the incorrect study treatment for the entire period of treatment, in which case the subject’s treatment group “as treated” will be defined as the incorrect study treatment.

Unless otherwise specified, the safety analysis will be based on the treatment group “as treated”.

### 6.2.1 Stratification

Subjects were stratified based on 4 different variables:

- PD-L1 Expression: PD-L1 $\geq$ 1% tumor cell surface expression / PD-L1 $<$ 1% tumor cell surface expression (entered by vendor in IRT)
- LAG-3 Status: LAG-3 $\geq$ 1% expression / LAG-3 $<$ 1% expression (entered by vendor in IRT)
- BRAF Status: Mutation Positive/ Mutation Wild-type at screening
- AJCC M Stage: M0/M1any[0] / M1any[1] at screening

During the monitoring of prospectively-assessed PD-L1 status, results revealed a lower rate of positivity (30-40%) than observed in historical studies of melanoma subjects (55-65%). Details regarding the initial scoring of PD-L1 at randomization vs. the historical rates of positivity

in melanoma studies can be found in the electronic protocol master file. The observed difference was hypothesized to be due to the testing site’s pathologists as all previous data was generated at [REDACTED] and the study CA224047 data was generated at [REDACTED].

To address the impact on efficacy assessment within the PD-L1/LAG-3-defined biomarker subsets included as secondary endpoints for Phase 2, [REDACTED] will enable re-scoring of PD-L1 by pathologists from a second testing site [REDACTED] for any randomized subjects who had been evaluated for PD-L1 at the [REDACTED] site. The re-scored PD-L1 results will be used in the primary efficacy analyses. If a rescore value is not applicable, indeterminate, or missing, it will be grouped together with PD-L1<1% and categorized as PD-L1<1% /non-quantifiable tumor cell surface expression if the number accounts for < 5% of the scores among all randomized subjects. If the number of non-quantifiable PD-L1 scores accounts for >=5% of the scores among all randomized subjects, they should be placed in a third category of PDL1 NON-QUANTIFIABLE and analyzed as such.

The evaluations of PD-L1 status were changed to [REDACTED] site at the start of Phase 3 so all subjects randomized during Phase 3 were scored via [REDACTED] pathologists at the [REDACTED] site. Thus, the PD-L1 values within the IRT system for all Phase 3 subjects will be used for the primary efficacy analyses. In addition, two subjects who transferred into the study during Phase 2 will also use the PD-L1 value placed in IRT. A sensitivity analysis will be performed using the IRT PD-L1 original scores for all subjects to assess the impact of the discrepancies.

During the monitoring of M-stage stratification, results showed that sites were not including LDH lab values into their classification. For this reason, the analyses will use the RAVE database for the M-stage stratification factor.

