- e) Tumor tissue from an unresectable or metastatic site of disease must be provided for biomarker analyses. Either a recent archival sample obtained within 3 months prior to enrollment (with no intervening treatment between time of acquisition and enrollment) or a fresh pre-treatment biopsy is to be submitted as a FFPE tissue block or unstained tumor tissue sections, to the analytical laboratory for inclusion. In order to be randomized, a participant must be classified as PD-L1 positive or PD-L1 negative, as well as LAG-3 positive or LAG-3 negative. Participants with indeterminate or unevaluable PD-L1 or LAG-3 status results will not be permitted to randomize to a treatment arm. If an insufficient amount of tumor tissue from an unresectable or metastatic site is available prior to the start of the screening phase, participants must consent to allow the acquisition of additional tumor tissue during the screening period for performance of biomarker analyses. The biopsy should be a core biopsy, a punch biopsy, an excisional biopsy, or a surgical specimen. Fine needle aspiration is unacceptable for submission. The analytical laboratory must provide IRT with the related results prior to randomization.
- f) Participants must have known BRAF V600 mutation status or consent to BRAF V600 mutation testing per local institutional standards during the screening period.
- g) Prior radiotherapy must have completed at least 2 weeks prior to study treatment administration.
- h) Participant Re-enrollment: This study permits the re-enrollment of a participant that has discontinued the study as a pre-treatment failure (ie, participant has not been randomized). If re-enrolled, the participant must re-consent.

3) Age and Reproductive Status

- a) Male and female participants must be ≥ 12 years at the time of informed consent if local regulations and/or institutional policies allow for participants < 18 years of age (pediatric population). If pediatric population is not allowed to participate, then ≥ 18 years applies.

- b) WOCBP must have a negative serum or urine pregnancy test (minimum sensitivity 25 IU/L or equivalent units of HCG) within 24 hours prior to the start of study treatment.
- c) Women must not be pregnant or breastfeeding.

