## 2.2 Treatment Assignment

After the subject's initial eligibility is established and informed consent has been obtained, the subject must be enrolled into the study by accessing an Interactive Response Technologies web-based system (IRT) to obtain the subject number. Every subject that signs the informed consent form must be assigned a subject number in IRT. The investigator or designee will register the subject for enrollment by following the enrollment procedures established by BMS. The following information is required for enrollment:

- Date that informed consent was obtained
- Date of birth
- Sex at birth.

Once enrolled in IRT, enrolled subjects that have met all eligibility criteria will be ready to be randomized through the IRT. The following information is required for subject randomization:

- Subject number
- Date of birth
- PD-L1 Expression: PD-L1  $\geq$ 1% tumor cell surface expression vs. PD-L1 <1% tumor cell surface expression /non-quantifiable (entered at IRT)
- LAG-3 Status: LAG-3  $\geq$  1% expression/ LAG-3 <1% expression (entered at IRT)
- BRAF Status: Mutation Positive/ Mutation Wild-type at IRT
- AJCC M Stage: M0/M1any[0] / M1any[1]) at IRT

Subjects meeting all eligibility criteria will be randomized in a 1:1 ratio to BMS-986213 or Nivolumab monotherapy and stratified by PD-L1 expression level (PD-L1  $\geq$ 1% expression vs PD-L1 < 1% expression), LAG-3 expression (LAG-3  $\geq$  1% expression vs LAG-3 < 1% expression), BRAF (Mutation Positive/ Mutation Wild-type ) and M stage (M0/M1any[0] / M1any[1]). The randomization procedures will be carried out via permuted blocks within each stratum.

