#### Inadequate Performance Status at Baseline:

- ECOG > 1 for adults, Lansky performance < to 80% for adolescents
- Verify Target Population: Prohibited Prior Therapies/Required Prior Therapies not Received  
No prior systemic anticancer therapy given as primary therapy for unresectable or metastatic disease (except anti PD-1, anti CTLA-4, BRAF- or MEK- inhibitor-containing regimens as adjuvant or neoadjuvant with at least 6 months between the last dose and the recurrence and interferon with at least 6 weeks prior to randomization). No Prior Treatment with Relatlimab or any other LAG-3 agents
- LAG-3, PD-L1, or BRAF mutation status unevaluable, indeterminate or not available prior to randomization. Note PD-L1 values should be based off of the IRT information and not the re-scored value. PD-L1 was re-scored posthoc and should not be considered an ineligibility if the value is non quantifiable.

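### Unavailable PD-L1 rescores default to the <1%/non-quantifiable group without use of the original IRT score, so IRT-positive participants can enter the PD-L1 <1% subgroup

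*SAP*

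**What the plan says.** SAP 6.2.1 (Stratification) explains the rescoring: during monitoring, "results revealed a lower rate of positivity (30-40%) than observed in historical studies of melanoma subjects (55-65" per cent). Specimens first read at the original site are to be read again by pathologists from a second site, and the rescore is used in the primary efficacy analyses. When the rescore fails, "If a rescore value is not applicable, indeterminate, or missing, it will be grouped together with PD-L1<1" per cent. The pooled level is labelled as including "non-quantifiable tumor cell surface expression if the number accounts for < 5% of the scores among all randomized subjects". At or above 5%, "they should be placed in a third category of PDL1 NON-QUANTIFIABLE and analyzed as such".

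Participants randomized in Phase 3 keep their IRT value, because scoring had moved to a different site by then. In addition, "two subjects who transferred into the study during Phase 2 will also use the PD-L1 value placed in IRT". A sensitivity analysis with the original IRT PD-L1 scores for all subjects is planned.

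On entry, Protocol 6.1 (criterion 2e) states: "Participants with indeterminate or unevaluable PD-L1 or LAG-3 status results will not be permitted to randomize to a treatment arm". Protocol Table 2-1 and section 7.2 say the same in other words: a positive or negative PD-L1 result goes from the laboratory to the IRT before randomization.

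The variable stratifies the PFS, OS and ORR tests (SAP 7.5). It also defines the PD-L1 and LAG-3 by PD-L1 subgroups for PFS, OS and ORR (SAP 7.5.3, 7.5.5, 7.5.8), where the low level again includes non-quantifiable results.

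**The concern.** A failed rescore says nothing about whether the tumour is positive or negative. The plan nevertheless treats it as a low result, or as a class of its own if there are enough of them, and sets aside a score that should already exist. The motive for rescoring was that the first site seemed to find too few positives. If so, its negative calls are the doubtful ones and its positive calls the more credible. The rule leaves the doubtful calls where they were and reverses the credible ones.

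What is at stake is the reading of the subgroup results. SAP 6.2.1 gives the PD-L1/LAG-3 subsets as the reason for rescoring, and a low-expression subgroup that contains IRT-positive participants blurs the contrast that the rescoring was meant to sharpen.

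**Working it through.** **1. Inputs.** About 700 randomized, of whom about 400 are in Phase 2 and can have a rescore (SAP 5). Pooling threshold below 5% of all randomized; positivity 30-40% at the first site and 55-65% historically (SAP 6.2.1). The plan gives no count of failed rescores, so everything below is a bound or a range.

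**2. Number affected by pooling.** 5% of 700 is 35, so the largest count under the threshold is 34. That is 34/700 = 4.9% of all randomized and 34/400 = 8.5% of those who can have a rescore. IRT-positive among them: 0.30 x 34 = 10.2 to 0.40 x 34 = 13.6, or about 10-14.

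**3. Direction of the error.** Let p be the true positivity in these specimens, s the chance that the first site calls a true positive positive, and f the chance that it calls a true negative positive. The probability that an IRT-positive participant is truly positive is

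PPV = s p / [s p + f (1 - p)].

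Assume that p equals the historical 0.55-0.65.
- If the original call carried no information (s = f), PPV = p = 0.55-0.65, already above one half.
- If s exceeds f, PPV is higher than p.
- If the site made no false positive calls (f = 0), PPV = 1.

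Moving n IRT-positive participants from low to high changes the number correctly classed by n(2 PPV - 1):
- s = f: 10.2 x (2 x 0.55 - 1) = 1.0 to 13.6 x (2 x 0.65 - 1) = 4.1.
- f = 0: 10.2 to 13.6.

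The expected gain at the cap is therefore between about 1 and 14 participants. IRT-negative participants stay in the low group under either rule.

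**4. Effect on the PD-L1 <1% subgroup.** The share of positives in the low group is c = moved / (negatives + moved).
- Positivity 30%: 10.2 / (490 + 10.2) = 2.0%.
- Positivity 40%: 13.6 / (420 + 13.6) = 3.1%.
- Positivity 55%: 18.7 / (315 + 18.7) = 5.6%.
- Positivity 65%: 22.1 / (245 + 22.1) = 8.3%.

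The last two lines count all participants among the 34 who would be positive at the historical rate; the IRT fallback could recover only those whom the first site called positive.

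For illustration, assume a true hazard ratio of 0.60 in negatives and h = 0.90 to 1.00 in positives, averaged on the log scale: HR = exp[(1 - c) ln 0.60 + c ln h]. With c = 2.0% and h = 0.90 this is 0.605; with c = 8.3% and h = 1.00 it is 0.626. If the two subgroups share one hazard ratio, nothing changes.

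**5. Effect on the primary test.** The plan's 85% power reproduces: sqrt(365)/2 x |ln 0.73| - 1.96 = 3.006 - 1.960 = 1.046, which gives 85.2% (85.0% at the 0.049 level). The PD-L1 rule does not enter that formula. A simulation of 3,000 trials used a log-rank test stratified by PD-L1, with 40% positive, a prognostic hazard ratio of 0.6 for positives, and 34 of 400 Phase 2 participants forced into the low stratum. Power was 84.7% with true strata and 84.6% with pooling; type I error was 5.4% and 5.3%. These are equal within simulation error.

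**The case against.** The strongest case for the plan is that it avoids returning to a source it has chosen to set aside. Falling back to the original score puts two scorers into one variable. That is a real, small cost, confined to the participants affected.

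Some stronger readings of the problem also fail.
- A reader might infer that every participant has a valid IRT result. That is an entry rule. SAP 2.2 labels the low IRT level as including "tumor cell surface expression /non-quantifiable (entered at IRT"), and SAP 7.2.1 lists as a deviation "LAG-3, PD-L1, or BRAF mutation status unevaluable, indeterminate or not available prior to randomization". Such participants would stay non-quantifiable under the fallback too, so this limits its reach without undoing it.
- A reader might call the misplaced participants known positives. They are positive by the scoring under question, and SAP 6.2.1 only hypothesizes that the site's pathologists explain the difference. Step 3 needs only the weaker statement that they are more likely positive than not.
- A reader might cite the use of IRT values in Phase 3 as precedent. It is none, because scoring had moved site. For the two transfers the SAP gives no reason.

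The plan has safeguards: the all-IRT analysis in 6.2.1, the PFS analysis with original IRT strata in 7.5, and a cross-tabulation by arm of original against rescored PD-L1 in 7.3.2. The first two do not isolate this problem, because they restore the questioned score for every rescored participant and so change much more than the failed rescores. The cross-tabulation would help if it shows failed rescores separately. PD-L1 is also the first stratification factor dropped if strata are small (7.5).

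Finally, timing. SAP 5.2.1 records that PFS was tested on 09MAR2021 and that the result led to subject-level unblinding. Redefining a stratification factor after that would be hard to defend. This stands, and the fix respects it.

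**Conclusion.** The point holds in limited form. The rule makes no use of an original PD-L1 result that randomization required, and it can place IRT-positive participants in the <1% subgroup. Pooling affects at most 34 of 700, about 10-14 of them IRT-positive if the first site's rate applies to these specimens. The fallback would correct between about 1 and 14 classifications at that cap, assuming the historical 55-65% applies to specimens that could not be rescored. With fewer failures all these figures shrink in proportion.

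It would be wrong to infer that the primary PFS result is in doubt: the simulated effect on power and type I error is negligible. Nor does any formal Phase 3 claim rest on the subgroups. Protocol Table 4-1 lists them as exploratory, and SAP 5.2.1 tests no endpoints formally beyond PFS, OS and ORR. The effect on them is modest, but it is avoidable.

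**What to change.** **Subgroup analyses (PD-L1 and LAG-3 by PD-L1).** When the rescore is not applicable, indeterminate or missing, use the original IRT/central-laboratory PD-L1 score. Apply this at the 5% and 10% cut-offs as well, where a numeric score exists. Keep non-quantifiable only for participants with no valid score from either site.

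**Stratified PFS, OS and ORR tests.** Keep the prespecified rule as primary. Add one supplementary analysis with the IRT fallback, labelled as specified after the PFS test and unblinding.

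**Reporting.** Give the number of participants with an unavailable rescore by arm and by original IRT status; a separate row in the cross-tabulation of SAP 7.3.2 would do.

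The cost is a short SAP amendment, a change to one derivation and one extra set of outputs, with no new data. The price in interpretation is that a few participants carry a score from the first site, which a footnote can state.
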